#### 2.8. Prior and Concomitant Medications

Medications will be classified as being prior, concomitant to piflufolastat (18F), and/or concomitant to flutufolastat (18F) and are defined as:

- Prior medications are defined as medications with a start date prior to the administration of piflufolastat (18F).
- Concomitant to piflufolastat (18F) medications are defined as medications that are ongoing at the administration of piflufolastat (18F) or have a start date after the administration of piflufolastat (18F).
- Concomitant to flutufolastat (18F) medications are defined as medications that are ongoing at the administration of flutufolastat (18F) or have a start date after the administration of flutufolastat (18F).

Medications may be included in multiple classifications.

## 2.9. Age

Age at informed consent in years will be derived based on the patient's year of birth:

$$\text{Year informed consent was signed} - \text{year of birth}$$

## 2.10. Overall Adjudicated Result

For all detection rate analyses, the detection rates will be calculated separately for each of the blinded readers, and also an overall adjudicated result where disagreements are resolved by a third independent read, allowing adjudication of disagreements by the majority read result.

## 2.11. General Conventions

Continuous data will be summarized using descriptive statistics for number of observations (n), mean, standard deviation (STD), median, 25th and 75th percentiles, minimum, and maximum. The minimum and maximum will be reported to the same number of decimal places (DPs) as the raw data recorded in the database. The mean, median, lower quartile and upper quartile will be reported to one more DP than the raw data and the STD will be reported to two more DPs than the raw data.

Frequencies and percentages will be used for summarizing categorical data. Percentages will be presented to one DP, apart from 100 which will be presented to 0 DP. Percentages will not be presented for zero counts.

P-values greater than or equal to 0.001 will be presented to three decimal places. P-values less than 0.001 will be presented as "<0.001".

## 2.12. Listings

Unless specified separately, listings will be created for the following only:

- Discontinued Patients
- PDs
- Patients Excluded from the Efficacy Analysis
- Demographic and Baseline
- Concomitant Medications
- Exposure to Flotufolastat (18F)
- Exposure to Piflufolastat (18F)
- Urinary Bladder SUVmean
- Positive Lesion Detection by Blinded Reader
- AEs; AEs Related to Flotufolastat (18F)
- Serious Adverse Events
- Deaths

## 2.13. Software

All analyses will be conducted using SAS Version 9.4 or higher.

### 3. Analysis Sets

For the purposes of analysis, the following analysis sets are defined:

**Table 2 Patient Analysis Sets**

Patient Analysis Set	Description
All Enrolled Patients	All patients who sign the Informed Consent Form.
Full Analysis Set (FAS)	All patients who receive either piflufolastat (18F) or flutufolastat (18F), and the corresponding PET scan is evaluable.
Full Safety Set (SAF)	All patients who receive either piflufolastat (18F) or flutufolastat (18F), regardless of whether the corresponding PET scan is performed.
Efficacy Analysis Set (EAS)	All patients who receive both piflufolastat (18F) and flutufolastat (18F), and the corresponding PET scans are evaluable.
Per Protocol Set (PPS)	All patients who receive both piflufolastat (18F) and flutufolastat (18F), and the corresponding PET scans are evaluable, and who are without any major PDs that will affect the evaluations of the PET scans.

The FAS, EAS and PPS will be used to analyse endpoints related to the efficacy objectives and the SAF will be used to analyse the endpoints and assessments related to safety.

### 4. Analyses Supporting Primary Objective

#### 4.1. Primary Endpoint

The primary endpoint for the study is the difference in urinary bladder  $SUV_{mean}$  between piflufolastat (18F) and flutufolastat (18F).

##### 4.1.1. Definition of Endpoint

The difference in urinary bladder  $SUV_{mean}$  will be calculated for each patient as:

$$Piflufolastat (18F) SUV_{mean} - Flutufolastat (18F) SUV_{mean}$$

A positive difference in urinary bladder  $SUV_{mean}$  represents a positive result (lower  $SUV_{mean}$ ) for flutufolastat (18F).

##### 4.1.2. Main Analytical Approach

Summary statistics for urinary bladder  $SUV_{mean}$  for piflufolastat (18F), flutufolastat (18F) and their differences will be presented in tables, box and whisker plots, scatter plots (flutufolastat on x-axis and piflufolastat on y-axis) and Bland-Altman plots (difference in urinary bladder  $SUV_{mean}$  against their average).

To test the statistical hypothesis specified in [Section 2.1](#), the data will first be checked for normality via. histograms and quantile–quantile (Q-Q) plots. The hypothesis will then be tested using either:

- If the difference in  $SUV_{mean}$  is non-normal, a two-sided paired Wilcoxon signed-rank test will be used to test the difference in urinary bladder  $SUV_{mean}$  between piflufolastat (18F) and flotufolastat (18F).
- If the difference in  $SUV_{mean}$  is normal, a two-sided paired t-test will be used to test the difference in urinary bladder  $SUV_{mean}$  between piflufolastat (18F) and flotufolastat (18F).

All analyses will be performed for all patients in the EAS. As all patients in the EAS will have both PET scans evaluable, there will be no missing data in this analysis.

#### **4.1.3. Sensitivity Analysis 1 – Per Protocol Set**

To assess the sensitivity of the intercurrent event specified in [Section 2.3.1](#), the first sensitivity analysis for the difference in urinary bladder  $SUV_{mean}$  will be done by repeating the primary analysis table on the PPS. This will exclude the patients from the primary analysis who had a major PD that may affect the evaluation of either PET scan.

#### **4.1.4. Sensitivity Analysis 2 – Patient Withdrawal After Piflufolastat [1]**

The second sensitivity analysis will assess the sensitivity of the intercurrent event specified in [Section 2.3.2](#). This will be done by repeating the primary analysis on the FAS and imputing missing flotufolastat urinary bladder  $SUV_{mean}$  with that patient's piflufolastat urinary bladder  $SUV_{mean}$ .

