### **2.3.2. Patient Withdrawal After Piflufolastat**

In the unlikely event that patients withdraw from the study after the piflufolastat PET scan but before flutufolastat scan, and therefore would have missing data for the flutufolastat scan, the patient withdrawal will be considered as an intercurrent event.

The following adjustments will be made in the primary analysis:

- Patients with only the piflufolastat PET scan will be excluded.

The following adjustments will be made as sensitivity analyses:

- Sensitivity Analysis 2: We will assume the data from the missing flutufolastat PET scan is the same as the piflufolastat PET scan.
- Sensitivity Analysis 3: We will assume the data from the missing flutufolastat PET scan is missing at random (MAR). A mixed model will be used and will include all available patient data.

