## 11. Sample Size Determination

Approximately 60 patients will be screened for inclusion into the study to obtain a minimum of 52 evaluable patients (i.e. have evaluable PET scans for both piflufolastat (18F) and flutufolastat (18F) available for analysis).

A sample size of 52 evaluable patients achieves 80% power to detect a mean of paired differences of 10 in  $SUV_{mean}$ , with an estimated STD of paired differences of 25 and with a significance level of 0.05 using a two-sided paired Wilcoxon signed-rank test assuming that the actual distribution of paired differences is uniform.

The difference in  $SUV_{mean}$  of 10 is based on the difference in the median bladder  $SUV_{mean}$  values of 25.4 observed for another renally cleared PSMA PET ligand, 68Ga-PSMA-11 (Kuten, et al., 2020) and 12.5 observed for flutufolastat (18F) (Kuo, et al., 2024).

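### Sensitivity Analysis 2 gives every withdrawn patient a paired difference of exactly zero, so its p-value cannot show sensitivity to withdrawal; only its estimates respond

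*SAP*

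**What the plan says.** SAP 2.3.2 treats withdrawal after the piflufolastat scan as an intercurrent event. The primary analysis leaves such patients out. Two sensitivity analyses bring them back, and the second in the SAP's numbering begins "Sensitivity Analysis 2: We will assume the data from the missing" flotufolastat scan equal the piflufolastat scan. SAP 4.1.4 puts this into operation: "This will be done by repeating the primary analysis on the FAS and imputing missing" flotufolastat bladder SUVmean with that patient's piflufolastat value.

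Three other sections decide what this does:

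- SAP 4.1.1 defines the difference as piflufolastat minus flotufolastat.
- SAP 4.1.2 checks normality and then chooses a test. If the differences are non-normal, "a two-sided paired Wilcoxon signed-rank test will be used to test the difference in urinary bladder" SUVmean; if they are normal, a two-sided paired t-test is used. Summary statistics and plots of the differences are also produced.
- SAP 2.13 says "All analyses will be conducted using SAS Version 9.4 or higher". Neither this section nor any other says how the signed-rank test is to treat zero differences.

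**The concern.** A sensitivity analysis for missing data should let the conclusion change if the missing values are unfavourable. Setting the second scan equal to the first makes the paired difference 0, and a zero carries almost no weight in either planned test. The signed-rank test in its classical form discards it before ranking. In the t-test, added zeros shrink the mean and its standard error nearly in proportion.

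If the report then states that the result was unchanged under Sensitivity Analysis 2, readers will take that as evidence that withdrawals did not matter. The agreement would in fact be built into the imputation rule.

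**Working it through.** **Inputs.** SAP 11 states the power claim: "A sample size of 52 evaluable patients achieves 80% power to detect a mean of paired differences of 10 in" bladder SUVmean. The same section takes the SD of the differences as 25 and sizes the trial for a two-sided signed-rank test at the 0.05 level under uniformly distributed differences. On recruitment it says "Approximately 60 patients will be screened for inclusion into the study". The number of withdrawals is therefore at most about 60 − 52 = 8 under the recruitment plan.

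**The plan's own figure.** The noncentrality is (10/25) × √52 = 2.884. A two-sided one-sample t power calculation at 0.05, taking the signed-rank test as fully efficient relative to t under a uniform distribution, gives 79.99% at n = 51 and 80.8% at n = 52. The stated 80% is reproduced, so mean 10, SD 25, n = 52 is a fair case to test.

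**Signed-rank branch.** With zeros dropped, the ranks come from the same 52 non-zero differences, so the statistic and p-value are those of the primary analysis. In a simulated data set with mean 10 and SD 25, p was 0.00872 with 0, 8, 26 and 52 zeros added. Pratt ranking, which keeps the zeros in the ranking, moves p only modestly with 8 zeros: 0.0087 to 0.0095 in that data set and 0.0046 to 0.0081 in one with uniform differences. Both stay far below 0.05.

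**t-test branch.** With n real differences and m imputed ones, N = n + m and

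t = √[(N − 1) r² / (N − r²)], where r² = (Σd)² / Σd².

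Adding zeros changes neither Σd nor Σd², so r² is fixed. Here Σd = 52 × 10 = 520 and Σd² = 51 × 25² + 52 × 10² = 37,075, so r² = 270,400 / 37,075 = 7.293.

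- m = 0: t = √(51 × 7.293 / 44.707) = 2.884, p = 0.0057.
- m = 8: t = √(59 × 7.293 / 52.707) = 2.857, p = 0.0059.
- m = 52: t = 2.787, p = 0.0063.
- As m grows without limit, t tends to √7.293 = 2.70, p about 0.0069.

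A borderline case behaves the same way: mean 7, SD 25 gives p = 0.0487 with no zeros and 0.0489 with eight. Solving the formula for p = 0.05 with SD 25 and eight zeros, significance is lost only if the primary p already lies between 0.04986 and 0.05.

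**What does move.** With eight zeros the mean falls to 520 / 60 = 8.67. In the first simulated data set above, the median fell from 9.8 to 3.5.

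**A shifted imputation.** If the missing flotufolastat value is the piflufolastat value plus delta, each imputed difference is −delta. For eight such patients on the t branch:

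| Case | N | Σd | Σd² | Mean | 95% CI | t | p |
|---|---|---|---|---|---|---|---|
| Primary, no imputation | 52 | 520 | 37,075 | 10.00 | 3.04 to 16.96 | 2.884 | 0.0057 |
| delta = 0 (as planned) | 60 | 520 | 37,075 | 8.67 | 2.60 to 14.74 | 2.857 | 0.0059 |
| delta = 5 | 60 | 480 | 37,275 | 8.00 | 1.85 to 14.15 | 2.603 | 0.012 |
| delta = 10 | 60 | 440 | 37,875 | 7.33 | 1.07 to 13.59 | 2.344 | 0.022 |
| delta = 25 | 60 | 320 | 42,075 | 5.33 | −1.42 to 12.09 | 1.579 | 0.12 |

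The interval is mean ± t(0.975, N − 1) × mean / t. For delta = 0 this is 8.667 ± 2.001 × 8.667 / 2.857.

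The signed-rank p depends on the particular data set. One simulated set gave about 0.013 at delta = 10 and 0.11 at delta = 25. Over 400 simulated normal samples, each scaled to mean 10 and SD 25, the median p was 0.044 at delta = 10 (10th to 90th percentile 0.023 to 0.084) and 0.18 at delta = 25 (0.12 to 0.27). In every one of these cases the planned analysis with zeros dropped would return the primary p.

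**The case against.** **The analysis is not empty.** A reader might infer that Sensitivity Analysis 2 cannot reveal anything. The documents do not support that. Repeating the primary analysis includes the summary statistics and plots of SAP 4.1.2, and these shrink towards zero. Equality of the two agents is also a recognisable conservative value for the estimate. This stands, and it confines the point to the hypothesis test.

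**Exact equality is conditional.** It needs the signed-rank branch and dropped zeros. The SAP states no zero rule. Nor does it say whether the normality check is repeated on the FAS, where a cluster of zeros could switch the test. This stands as well, although near-equality on the t branch needs no assumption about zeros.

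**Withdrawals will be few.** SAP 2.3.2 calls the event unlikely, the scans are at most 10 calendar days apart, and Protocol 13.2 allows additional recruitment. The 60 are patients screened, so the gap of eight also absorbs screen failures and non-evaluable scans. With four patients at delta = 25 the t-test p is 0.033 (Σd = 420, Σd² = 39,575, N = 56), still significant. This stands and limits the importance.

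**Large deltas look implausible.** A patient who leaves before the second scan cannot have left because of its value, and the protocol's rationale expects lower bladder activity with flotufolastat. That is a fair argument when judging the delta at which significance is lost. It is not a reason to omit the calculation.

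**Sensitivity Analysis 3 addresses the same event.** A reader might go further the other way and conclude that the trial has no working check on withdrawals, because that model fits treatment and period together in a fixed-order design. That is a separate matter for SAP 4.1.5, and this point does not depend on it.

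**Conclusion.** The point holds for the p-value of Sensitivity Analysis 2. On the signed-rank branch with zeros dropped, it equals the primary p for any number of withdrawals. On the t branch at the planning values it moves from 0.0057 to 0.0059 with eight. The hypothesis test therefore cannot show sensitivity to withdrawal, and agreement with the primary p is not evidence of robustness. The estimates do respond (mean 10 to 8.67).

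The figures assume mean 10, SD 25, 52 complete pairs and eight withdrawals, which is an upper bound. The primary analysis on the EAS is unaffected. Severity: minor.

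**What to change.** In SAP 4.1.4, and to match in 2.3.2, impute the missing flotufolastat SUVmean on the FAS as that patient's piflufolastat SUVmean plus delta, over a short pre-specified grid such as delta = 0, 5, 10 and 25. Positive delta is unfavourable to flotufolastat; 10 matches the planned difference and 25 the planned SD.

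- At each delta report the estimate and 95% CI (the mean difference on the t branch, the Hodges-Lehmann estimate on the signed-rank branch), and state the delta, if any, at which significance is lost.
- Interpret the delta = 0 row by its estimate and CI, not by its p-value.
- State how zero differences are handled, and whether the test chosen on the EAS is carried over to the FAS. Changing to Pratt ranking is not a remedy, since it also hardly moves p.

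The cost is a few lines of SAP text and code, with no new data, visits or patients. If nobody withdraws after the first scan, the analysis is simply not needed.

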#### **4.1.5. Sensitivity Analysis 3 – Patient Withdrawal After Piflufolastat [2]**

The third sensitivity analysis will assess the sensitivity of the intercurrent event specified in [Section 2.3.2](#). This will be done by using a mixed effects linear model fitted to the data for urinary bladder  $SUV_{mean}$  between piflufolastat (18F) and flotufolastat (18F). The model will include fixed effect terms for treatment and period, and a random effect for the patient. The least squares means and 95% confidence intervals (CIs) for the treatment groups and estimated differences will be determined and provided, and the FAS will be used. Any missing data will be assumed MAR and maximum likelihood estimation will be used to fit the model parameters.

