9.1.4 Imaging Studies

All patients will receive the PSMA PET scans in the following order: piflufolastat (^{18}F) (Scan 1; Visit 2) and flutufolastat (^{18}F) (Scan 2; Visit 3). Further details of the imaging acquisition protocol are provided in [Section 11](#).

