### 1.2.1. Blinding

The local sites, including the investigator, will not be blinded as each patient will receive piflufolastat (18F) first as part of their routine clinical care (Day 1), followed at least 24 hours later, but within 10 calendar days, by flutufolastat (18F). For imaging interpretation, central readers will be blinded to the radiopharmaceutical and all other clinical data.

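### Sensitivity Analysis 3 fits treatment and period together in a one-sequence design, so its promised treatment means, difference and confidence intervals are not estimable as written

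*SAP*

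**What the plan says.** SAP section 4.1.5 defines Sensitivity Analysis 3, one of two analyses for patients who withdraw between the scans. On the model it says: "The model will include fixed effect terms for treatment and period, and a random effect for the patient". On the output: "The least squares means and 95% confidence intervals (CIs) for the treatment groups and estimated differences will be determined and provided". On estimation: "Any missing data will be assumed MAR and maximum likelihood estimation will be used to fit the model parameters". The analysis set is the Full Analysis Set (FAS), which SAP Table 2 defines as "All patients who receive either piflufolastat (18F) or flutufolastat (18F), and the corresponding PET scan is evaluable". It can therefore include patients with one scan.

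SAP section 2.3.2 describes the same analysis as a mixed model on all available patient data and does not mention period.

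The order of the scans is fixed. Protocol section 9.1.4 says "All patients will receive the PSMA PET scans in the following order" and lists piflufolastat as Scan 1 and flotufolastat as Scan 2. SAP section 1.2.1 says that "each patient will receive piflufolastat (18F) first as part of their routine clinical care (Day 1), followed at least 24 hours later" by flotufolastat. Protocol sections 8.1, 8.2 and 8.7 and footnote b of Protocol Table 1 agree. Neither document describes a reverse sequence or randomisation of order, and the SAP does not define period in any other way.

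**The concern.** A period term can be separated from a treatment term only if some patients receive the treatments in a different order from others. Here none do. Period 1 is always piflufolastat and period 2 is always flotufolastat, so the data cannot divide the scan-to-scan difference between tracer and order.

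Two things are at stake. First, this is the only analysis of the primary endpoint that treats missing flotufolastat scans as missing at random; Sensitivity Analysis 2 sets the missing difference to zero. Second, SAP section 4.1.2 gives summary statistics, plots and a hypothesis test for the primary difference but no confidence interval, so section 4.1.5 is the only place in the SAP text that promises one. If the model stays as written, someone has to decide at the programming stage what to report instead.

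**Working it through.** The SAP gives no figure for this analysis, so the check is one of estimability.

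**Design rows.** Code the fixed part as (intercept, piflufolastat, flotufolastat, period 1, period 2). Under the fixed order only two distinct rows can occur:

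- piflufolastat scan: r1 = (1, 1, 0, 1, 0)
- flotufolastat scan: r2 = (1, 0, 1, 0, 1)

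Separating the effects needs rank 3 (intercept, one treatment contrast, one period contrast). Two distinct rows give rank 2.

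**Estimability.** A contrast is estimable only if it equals a·r1 + b·r2 = (a+b, a, b, a, b).

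| Quantity | Contrast | Requirement | Estimable? |
|---|---|---|---|
| Piflufolastat LS mean | (1, 1, 0, ½, ½) | a = 1 and a = ½ | No |
| Flotufolastat LS mean | (1, 0, 1, ½, ½) | a = 0 and a = ½ | No |
| Treatment difference | (0, 1, −1, 0, 0) | a = 1 and a = 0 | No |
| Piflufolastat at Scan 1 minus flotufolastat at Scan 2 | (0, 1, −1, 1, −1) | a = 1, b = −1 | Yes |

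**Numerical check on three layouts.**

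- 52 complete pairs in the fixed order: rank 2; LS means and difference not estimable.
- 60 patients in the fixed order, 8 without Scan 2 (an illustrative split of the planned 60 screened and 52 evaluable): rank 2, same result. The treatment and period indicators have correlation 1.0. A one-scan patient still contributes r1 or r2, so incomplete pairs do not help.
- Control, 52 patients in a 1:1 two-sequence crossover: rank 3; every contrast estimable. The fixed order is therefore the cause.

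**Simulated fit.** One data set was generated with 60 patients, 8 lacking Scan 2. The assumed values were true means 25 and 15, between-patient SD 10 and residual SD 25/√2. The random-intercept model was fitted by maximum likelihood.

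- Without period: difference 12.19, standard error 3.37.
- With period: treatment 36.19, period 24.00, each with a standard error of about 1.9 × 10⁸. The fit is singular and the individual values are arbitrary.
- The combined contrast from the second fit is 36.19 − 24.00 = 12.19, the same as the difference without period.

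**Precision once period is removed.** The SAP section 11 planning values are 52 pairs, mean difference 10 and SD of differences 25:

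- standard error = 25/√52 = 3.47
- 95% half-width, t on 51 degrees of freedom = 6.96
- interval = 10 ± 6.96, or 3.04 to 16.96

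This is the complete-pairs value. One-scan patients and maximum likelihood variance estimation would change it somewhat.

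**The case against.** The case for leaving this alone, or treating it as minor, has real substance.

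- *It is a third sensitivity analysis for a rare event.* SAP section 2.3.2 itself calls withdrawal between scans unlikely. The primary test uses the Efficacy Analysis Set, where both scans are evaluable by definition, and does not use this model. Sensitivity Analysis 2 covers the same event with a conservative imputation. This stands and limits the severity.
- *The analysis does not fail entirely.* A reader might infer that the model yields nothing usable. The documents do not support that: the combined contrast stays estimable and is the paired difference defined in SAP section 4.1.1. What cannot be obtained is what section 4.1.5 promises, namely treatment means and a treatment difference with period in the model.
- *Software will cope.* It may report the quantities as non-estimable, or drop one term and label the combined contrast as treatment. The second outcome gives a sensible number, but from a model other than the one specified, and under a label suggesting that period has been accounted for.
- *Period might mean something else.* It is undefined, and the table specifications sit in a separate document. Scan order is nevertheless the only natural reading of the text.

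A reader might also infer that the model was taken from a randomised crossover, or that the sponsor claims to remove an order effect. Neither document says so, and both state the fixed order openly.

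**Conclusion.** The specification is wrong as written and should be fixed. With treatment and period both fixed and a single sequence, the rank is 2 against the 3 needed, and the promised LS means, difference and confidence intervals are not estimable. This is algebra: it does not depend on the sample size, the amount of missing data or the random patient effect. It rests on one assumption, that period means scan order.

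The scope is narrow. A reader might infer that the primary result is undermined by this error; it is not, because the primary test and Sensitivity Analyses 1 and 2 do not use the model. The primary difference also combines tracer and scan order, but that follows from the design and not from this specification. The absence of a confidence interval in section 4.1.2 makes the analysis worth repairing but does not raise the severity of the error.

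A reader might also infer that a different model could isolate the tracer effect. None can when there is only one sequence.

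**What to change.** In SAP section 4.1.5, delete the words 'and period', so that the model is SUVmean = treatment (fixed) + patient (random), fitted by maximum likelihood on the FAS as already planned. This agrees with the description in section 2.3.2 and keeps the analysis on the arithmetic difference used in sections 2.1 and 4.1.1.

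Add one sentence: tracer and scan order are completely confounded by design, so the estimated difference combines both and no period effect can be estimated or adjusted for.

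The cost is one line of wording and one added sentence. No new data and no change to the primary analysis are needed. Done before database lock it is an ordinary SAP correction; afterwards it is a departure that SAP section 1 requires to be documented in the study report.

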To evaluate the impact of urinary radioactivity on flutufolastat (^{18}F) PET/computed tomography (CT) image interpretation and disease assessment, *post hoc* analysis of the flutufolastat (^{18}F) PET scans from the two BED-sponsored prospective Phase 3 studies (Study BED-PSMA-301 [LIGHTHOUSE] and Study BED-PSMA-302 [SPOTLIGHT]) have been performed ([Kuo et al, 2024](#)). For this analysis, 718 flutufolastat (^{18}F) PET scans, (352 from Study BED-PSMA-301 and 366 from Study BED-PSMA-302), were evaluated by three board-certified nuclear medicine readers trained to read flutufolastat (^{18}F) scans. For qualitative assessments, all three readers qualitatively assessed the impact of any urinary radioactivity in the bladder on image interpretation using a 3-point scale (0=no/minimal visible urinary radioactivity, 1=urinary radioactivity visible but distinction between urine and disease possible, and 2=assessment inhibited by urinary radioactivity), and the presence/absence of ureteric radioactivity and halo artifacts. Quantitative assessments (maximum standardized uptake value [SUV_{max}] and mean standardized uptake value [SUV_{mean}]) of bladder radioactivity were also performed, by placing a circular region of interest over the maximum diameter of the bladder radioactivity in the transverse plane.

Of the 718 eligible scans, 712 were evaluable for bladder radioactivity (348 with newly diagnosed prostate cancer; 364 with BCR of prostate cancer). Six scans were excluded from the evaluation due to cystectomy, renal failure, and urinary catheter in situ (two scans each). The median SUV_{max} in the bladder was 17.1 (interquartile range: 9.2, 28.3) and median SUV_{mean} was 12.5 (interquartile range: 7.0, 19.3; [Figure 2](#)).

Figure 2: Quantitative Assessment of Bladder Radioactivity: SUV_{max} and SUV_{mean}

Abbreviations: SUV=standardized uptake value; SUV_{max} =maximum standardized uptake value; SUV_{mean} =mean standardized uptake value.

Source: [Kuo et al, 2024](#)

[figure not shown]

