15.1 Estimation of Sample Size

Approximately 60 patients will be screened for inclusion into the study to obtain a minimum of 52 evaluable patients (i.e., have evaluable PET scans for both piflufolastat (^{18}F) and flotufolastat (^{18}F) available for analysis).

A sample size of 52 evaluable patients achieves 80% power to detect a mean of paired differences of 10 in SUV_{mean} , with an estimated standard deviation of paired differences of 25 and with a significance level of 0.05 using a two-sided paired Wilcoxon signed-rank test assuming that the actual distribution of paired differences is uniform.

The difference in SUV_{mean} of 10 is based on the difference in the median bladder SUV_{mean} values of 25.4 observed for another renally cleared PSMA PET ligand, ^{68}Ga -PSMA-11 (Kuten et al, 2020) and 12.5 observed for flotufolastat (^{18}F) (Kuo et al, 2024; see Figure 3, Section 1.3).

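### Sensitivity Analysis 3 cannot be estimated with its period term, and once that is dropped its unstated covariance defaults to one variance for both tracers, which the plan's figures make unlikely

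*SAP*

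**What the plan says.** Sensitivity Analysis 3 (SAP 4.1.5) addresses patients who withdraw after piflufolastat and before flotufolastat. It fits a linear mixed model to bladder SUVmean in the FAS, with missing values assumed missing at random. On the model terms: "The model will include fixed effect terms for treatment and period, and a random effect for the patient". On estimation: "maximum likelihood estimation will be used to fit the model parameters". On output: "The least squares means and 95% confidence intervals (CIs) for the treatment groups and estimated differences will be determined and provided". The section gives no residual covariance structure and no tracer-specific variance.

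Three other places bear on it:

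- Protocol 8.1 and 9.1.4 fix the scan order: piflufolastat first, flotufolastat second, for every patient.
- Protocol 1.3 gives the only SUVmean spread for either study tracer. For flotufolastat the median is 12.5, with "interquartile range: 7.0, 19.3", from 712 evaluable scans in two earlier studies.
- Protocol 15.1 and SAP 11 size the trial "with an estimated standard deviation of paired differences of 25". No source is given for the 25.

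**The concern.** Two features of the model sentence cause trouble.

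First, a period effect can be separated from a tracer effect only if some patients receive the tracers in the other order. None do.

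Second, with period removed, a patient random intercept and a single residual variance give both tracers the same total variance. If piflufolastat bladder SUVmean varies much more than flotufolastat SUVmean, the fit averages the two variances. The piflufolastat interval is then too short and the flotufolastat interval too long. The same averaging distorts the regression by which an observed piflufolastat value informs a missing flotufolastat value, and that recovery is the reason for the analysis.

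At stake are the per-tracer means and intervals, a pre-specified output on the primary variable. Leaving the covariance unstated also leaves a modelling choice open until the data are in hand.

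**Working it through.** **The plan's own figure.** With mean difference 10, SD 25 and two-sided alpha 0.05, the normal approximation gives ((1.960 + 0.842) × 25/10)² = 49.1, so 50. A noncentral-t calculation for the paired test, with Wilcoxon efficiency 1 for uniform differences, gives 79.99% power at 51 and 80.8% at 52. The planned 52 is reproduced by that route, so 25 is the SD the plan works with. (Direct simulation of the signed-rank test on uniform differences gave 74.5% power. That is a separate matter and does not affect this point.)

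**Estimability.** With an intercept, two treatment columns and two period columns, every piflufolastat row is identical and so is every flotufolastat row. The design matrix has rank 2; a design using both orders would have rank 3. Neither the per-tracer least-squares means nor the treatment difference is estimable. Only the sum of the treatment and period contrasts is. Everything below assumes that period has been dropped.

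**Flotufolastat SD (SDf), from the quartiles.**

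- Normal: (19.3 − 7.0)/1.349 = 9.1.
- Lognormal: s = ln(19.3/7.0)/1.349 = 0.752, so SDf = 12.5 × exp(s²/2) × √(exp(s²) − 1) = 14.5.

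**Is a common variance compatible with 25?** If both SDs equal σ, then 25² = 2σ²(1 − ρ), so σ = 25/√(2(1 − ρ)). This is 17.7 at ρ = 0 and larger for positive ρ. A patient random effect implies ρ ≥ 0, so a common SD must be at least 17.7, above both 9.1 and 14.5. Setting σ equal to SDf instead requires ρ = 1 − 625/(2·SDf²), which is −2.8 (impossible) for 9.1 and about −0.50 for 14.5.

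**Implied piflufolastat SD (SDp).** Solve 625 = SDp² + SDf² − 2ρ·SDp·SDf. The documents give no ρ; 0 to 0.75 is assumed. The common-variance fit uses pooled SD = √((SDp² + SDf²)/2) for both tracers. Interval width relative to correct is pooled/SD for that tracer, and coverage is 2Φ(1.96 × pooled/SD) − 1.

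| SDf | ρ | SDp | Pooled SD | Piflufolastat width (coverage) | Flotufolastat width (coverage) |
|---|---|---|---|---|---|
| 9.1 | 0 | 23.3 | 17.7 | ×0.76 (86%) | ×1.9 (>99.9%) |
| 9.1 | 0.75 | 31.1 | 22.9 | ×0.74 (85%) | ×2.5 (100%) |
| 14.5 | 0 | 20.4 | 17.7 | ×0.87 (91%) | ×1.2 (98%) |
| 14.5 | 0.75 | 33.9 | 26.1 | ×0.77 (87%) | ×1.8 (>99.9%) |

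**Simulation check.** Normal data, ρ = 0.25, maximum likelihood, 150 runs per scenario (Monte Carlo error 2 to 3 points):

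- Common-variance coverage was 87 to 91% for piflufolastat and 99 to 100% for flotufolastat.
- Coverage for the difference was 95 to 96% with 52 complete pairs, and 94% with 60 piflufolastat and 52 flotufolastat scans.
- With 52 pairs and SDf = 9.1, half-widths moved from 5.2 for both tracers to 6.9 (piflufolastat) and 2.5 (flotufolastat) under an unstructured covariance. With SDf = 14.5 they moved from 5.4 for both to 6.6 and 3.9. The half-width for the difference stayed at about 6.7.
- With 60 and 52 scans, the unstructured fit under maximum likelihood and a 1.96 multiplier covered 91 to 92% for flotufolastat and 92% for the difference. That is one reason to pair it with REML and small-sample degrees of freedom.

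**Recovery slope at ρ = 0.3.** The model's slope is ρ·SDp·SDf/pooled²; the correct slope is ρ·SDf/SDp.

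- SDf = 9.1, SDp = 26.2: 0.19 against 0.10.
- SDf = 14.5, SDp = 25.2: 0.26 against 0.17.

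Suppose six of 58 patients lack Scan 2 and their piflufolastat values differ from completers' by 10. With SDf = 9.1, the flotufolastat mean shifts by about (0.186 − 0.105) × 10 × 6/58 = 0.08. In a deliberately extreme simulation, where the six highest piflufolastat values lack Scan 2, the common-variance bias was about +1.0 SUV, and the unstructured estimate was nearly unbiased.

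**The case against.** Several points on the other side are sound.

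- **The SAP does not state equal variances.** A reader might infer that it does. It is silent, and table specifications sit in a separate document (SAP 1). The defect is an unspecified covariance with an equal-variance default.
- **The figures do not prove unequal variances.** The documents give no SUVmean level or spread for piflufolastat, only SUVmax. The interquartile range is external and slightly skewed. It mixes newly diagnosed and recurrent disease, and was measured with a circular region in one plane rather than a volume of interest. The 25 is unsourced. With skewed data and a correlation near −0.5, equal variances are possible. So the intervals are likely to be miscalibrated, not certain to be.
- **The simulated data are idealised.** Normal data with these means and SDs include some negative SUVs. The width ratios follow from the SDs alone, but the coverage figures are approximate.
- **The study question is barely touched.** A reader might infer that the tracer comparison is compromised. The primary test is a signed-rank or paired t-test in the EAS and does not use this model. Coverage for the difference stays near nominal, and each tracer's own SD and quartiles are tabulated separately under SAP 4.1.2.
- **The missing-data harm is small unless dropout is strongly selective.** SAP 2.3.2 regards withdrawal as unlikely, and six withdrawals is an assumption.

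All of this limits the size of the point. None of it makes the written model estimable or supplies the missing covariance.

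**Conclusion.** The point holds as a minor defect in one sensitivity analysis. The aliasing of period with treatment follows directly from the fixed scan order and needs no assumption. The variance point is an inference from two planning figures, and holds under both the normal and the lognormal reading when within-patient correlation is non-negative. For correlations of 0 to 0.75, the piflufolastat interval would be about 13 to 26% too narrow and the flotufolastat interval about 1.2 to 2.5 times too wide. The recovery slope is too steep whenever the correlation is positive. Maximum likelihood itself adds little: standard errors about 1% too small, √(51/52) = 0.990.

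The documents do not support concluding that the primary result, or the estimated difference with complete pairs, is at risk.

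**What to change.** In SAP 4.1.5:

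1. Remove the period term and say why: with one scan order, the estimated difference contains any period effect and the two cannot be separated.
2. Replace the patient random intercept with an unstructured 2x2 within-patient covariance by tracer (in SAS, PROC MIXED with a REPEATED statement and TYPE=UN).
3. Fit by REML with Kenward-Roger degrees of freedom in place of maximum likelihood.
4. Keep the missing-at-random assumption and the FAS.

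Step 2 alone is not enough, because the least-squares means stay non-estimable while period remains. The cost is a short edit to one section and its program, with no new data, no extra patients and no change to the primary analysis.
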